## 8. MANAGEMENT ALGORITHMS FOR TOXICITIES

### 8.1 DOSING DELAYS/DOSE DISCONTINUATION

The following ADRs require permanent treatment discontinuation of avelumab:

- Any Grade 4 ADRs require treatment discontinuation with avelumab except for single laboratory values out of normal range that are unlikely related to study treatment as assessed by the Investigator, do not have any clinical correlate, and resolve within 7 days with adequate medical management. Patients who experience grade IV toxicity will continue to be followed until toxicity resolution to Grade  $\leq 1$  or return to baseline.

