### 11.2 Definitions

Evaluable Population: will consist of all patients who have received 1 cycle of CBI treatment preceding SBRT.

Safety Population: Will consist of all subjects who were enrolled and have received CBI combined with SBRT. This will be used to assess the clinical safety and tolerability of the study.

Evaluable for Objective Response: Only those patients who have measurable disease present at baseline, have completed all fractions of SBRT, and have had their disease re-evaluated will be considered evaluable for response. These patients will have their response classified according to the definitions stated below.

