### **11.5.3 Clinical Response Parameters**

**Time to Local Progression (TTLP)** is defined as the elapsed time from the start of treatment to the date of documented local progression or death, whichever happens earliest.

**Relapse-Free Survival (RFS)** is defined as the time from starting treatment to the time of first documented tumor progression or death due to any cause, whichever occurs first. Death is considered as an event here. For subjects whose disease does not progress or who do not die, PFS will be censored at the time of the last visit.

**Time to Progression (TTP)** is defined as the time from starting treatment to the time of first documented tumor progression. Subjects who do not progress will be censored at the time of the last contact. In addition, death from any cause will also be censored.

**Overall Survival (OS)** is defined as the time from starting treatment until death due to any cause. For subjects who do not die, time to death will be censored at the time of last contact.

**Locoregional Control (LRC)** is defined as the time from starting treatment until local and/or regional relapse is documented

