### 15.4 Analysis of Primary Objectives

Phase I: If no more than one-third of the subjects permanently discontinue study medication prior to completing six doses due to treatment related adverse events then this combination will be deemed as tolerable and return to the IRB, DMC, and Sponsor for further evaluation and approval prior to proceeding to the Phase II cohort.

If  $\geq 4$  patients in the Phase I cohort permanently discontinue study medication prior to completing six doses due to treatment related adverse events then we will suspend the study and return the study to the IRB and DSMB committees for further evaluation and recommendations.

Phase II: The primary efficacy analysis will be the relapse free survival (RFS) rate in patients with early Stage NSCLC receiving SBRT combined with concurrent and adjuvant Avelumab compared to SBRT alone historical controls. The analysis population includes all registered subjects who have received SBRT and at least 2 cycles of Avelumab.

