### **15.7 Evaluation of Response**

All patients included in the study must be assessed for response to treatment, even if there are major protocol treatment deviations or if they are ineligible. Each patient will be assigned one of the following categories: 1) complete response, 2) partial response, 3) stable disease, 4) progressive disease, 5) early death from malignant disease, 6) early death from toxicity, 7) early death because of other cause, or 8) unknown (not assessable, insufficient data).

All of the patients who met the eligibility criteria (with the possible exception of those who received no study medication) should be included in the main analysis of the response rate. Patients in response categories 4-8 should be considered to have a treatment failure (disease progression).

All conclusions should be based on all eligible patients. Sub-analyses may then be performed on the basis of a subset of patients, excluding those for whom major protocol deviations have been identified (e.g., early death due to other reasons, early discontinuation of treatment, major protocol violations, etc.). However, these sub-analyses may not serve as the basis for drawing conclusions concerning treatment efficacy, and the reasons for excluding patients from the analysis should be clearly reported. The reason for performing subset analyses would be to generate hypotheses for future prospective clinical trials.

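### The primary RFS analysis in 15.4 admits only patients who received SBRT and a second avelumab cycle, so entry depends on events after the RFS clock starts; 11.2 and 15.7 describe other populations

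*Combined protocol and SAP*

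**What the plan says.** Section 15.4 fixes the population for the Phase II primary RFS comparison: "The analysis population includes all registered subjects who have received SBRT and at least 2 cycles of Avelumab". It does not say whether any SBRT fraction is enough or all are needed.

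RFS in 11.5.3 "is defined as the time from starting treatment to the time of first documented tumor progression or death due to any cause". Treatment starts with avelumab cycle 1. The first SBRT fraction follows 3-10 days later (6.3.2), and cycle 2 is due 14 days after cycle 1 (6.3.1).

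The protocol itself takes some patients off the drug early. Section 8.1 states: "Any Grade 4 ADRs require treatment discontinuation with avelumab except for single laboratory values out of normal range" (with further conditions on that exception). It applies the same to Grade 3 reactions, with a list of exceptions. Section 8.2 ends study drug after any Grade 3 or 4 infusion reaction.

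Two other sections describe populations:

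- Section 11.2: "Evaluable Population: will consist of all patients who have received 1 cycle of CBI treatment preceding SBRT". No analysis is assigned to this set.
- Section 15.7: "All conclusions should be based on all eligible patients". It then allows subset analyses that leave out patients for reasons such as "early death due to other reasons, early discontinuation of treatment, major protocol violations", but says that "these sub-analyses may not serve as the basis for drawing conclusions concerning treatment efficacy". Another sentence of 15.7 is narrower: eligible patients "should be included in the main analysis of the response rate".

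Section 15.2 plans 56 patients including 10% dropout, and 80% power for 2-year RFS of 90% against 80%, using a one-sided t-test at 0.10. Section 15.4 names no test.

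**The concern.** Membership of the primary set is decided after time zero by receipt of SBRT and a second infusion. The patients removed are not a random sample: they include those taken off avelumab for toxicity and those who did not reach or complete the local treatment. A trial judged against a fixed 80% has no control arm that loses comparable patients, so any difference in prognosis goes straight into the RFS estimate and the test.

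The plan also disagrees with itself. For early stoppers, 15.4 makes primary the kind of exclusion that 15.7 says cannot support an efficacy conclusion. If results differ between the sets, there is room to argue afterwards over which one carries the RFS conclusion.

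**Working it through.** **1. Which patients are lost.** Three routes need separating.

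- *Death or any RFS event before cycle 2.* At a constant hazard h = -ln(S)/730.5 per day, the expected number in 56 patients over 14 days is 56 × (1 - exp(-14h)). With S = 0.80 this is 0.24; with S = 0.90 it is 0.11. This route is small.
- *Progression before cycle 2.* It is lost only if cycle 2 is then not given. Section 6.7 does not list progression as a reason for removal, and the first scheduled scan after treatment start is at cycle 4 (6.2) or 6 weeks after SBRT (6.4). This route is small too.
- *Stopping avelumab after cycle 1, or never receiving SBRT.* All later RFS outcomes of these patients leave the primary analysis. This is the main loss.

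**2. How many, and how they fare.** The documents do not say. The avelumab study summarised in 4.2 reports drug-related Grade 3 or higher events in 22/184 (12%), including 4/184 infusion reactions (2.2%). These cover all infusions in advanced disease and are not rates of stopping after cycle 1. If all four infusion reactions had been at cycle 1 (an assumption), the same rate would give 56 × 4/184 = 1.2 patients.

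**3. Effect on the estimate and the test (illustration, assumed inputs).** The planned 56 less 10% is 50.4, so N = 50. True all-treated 2-year RFS is 0.80, the null. Let k patients be excluded, with 2-year RFS r, and n = 50 - k.

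- RFS among those kept: p = (0.80 × 50 - k × r)/n. For k = 3 and r = 0.50: (40 - 1.5)/47 = 0.819.
- Normal test: c = 0.80 + 1.2816 × sqrt(0.16/n); rejection rate = 1 - Φ((c - p)/sqrt(p(1 - p)/n)).
- Exact test: smallest x with P(X ≥ x | n, 0.80) ≤ 0.10, then P(X ≥ x | n, p).

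Both are shown because 15.4 names no test.

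| k excluded | r | RFS kept | Normal | Exact (rule) |
|---|---|---|---|---|
| 0 | – | 0.800 | 0.100 | 0.048 (45/50) |
| 1 | 0.80 | 0.800 | 0.100 | 0.055 (44/49) |
| 1 | 0.50 | 0.806 | 0.117 | 0.067 |
| 1 | 0.25 | 0.811 | 0.134 | 0.079 |
| 3 | 0.80 | 0.800 | 0.100 | 0.0705 (42/47) |
| 3 | 0.50 | 0.819 | 0.161 | 0.124 |
| 3 | 0.25 | 0.835 | 0.232 | 0.191 |

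Part of the exact rise is only the change in n: compare the r = 0.80 rows.

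**4. Other N.** Exact rates for r = 0.50 and 0.25: with N = 56, 0.070 and 0.081 (k = 1), 0.125 and 0.186 (k = 3); with N = 44, 0.063 and 0.075 (k = 1), 0.123 and 0.194 (k = 3). The choice of N hardly matters.

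**5. The passages side by side.** Section 15.4 requires SBRT and two cycles. The 11.2 Evaluable Population requires one cycle before SBRT. Section 15.7 uses all eligible patients. Section 15.5 plans Kaplan-Meier RFS estimates and names no population. No section says which rule governs RFS or plans an all-treated RFS analysis.

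**The case against.** The strongest case for leaving 15.4 alone runs as follows.

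- *Only 15.4 assigns a population to Phase II RFS, and a specific rule outranks general text.* Section 15.7 is headed as response evaluation and partly limited to the response rate; the 11.2 set is tied to no analysis. This stands in part: the reach of 15.7 to RFS is unclear. But its sentences on conclusions and on efficacy carry no such limit.
- *Requiring SBRT is defensible, because the comparator is SBRT alone.* This stands as a reason to keep the restricted set in the report. It does not justify the two-cycle condition, which removes patients who did receive SBRT.
- *The harm is small or hypothetical.* With one exclusion, the exact rejection rate (0.067 to 0.079) stays under the nominal 0.10. A patient who stops avelumab may still receive SBRT and match the planned 80%, in which case nothing is inflated. The RFS values of 50% and 25%, and the three-patient case, have no source in the documents. All of this stands and limits the size, not the direction if early stoppers do worse.
- *Taking 50 as all treated may count dropouts twice.* This is a fair point on the illustration, but N = 56 gives nearly the same rates.
- *Outcomes are not wholly lost.* Section 15.5 plans RFS summaries without the restriction, 11.5.3 censors event-free patients at the last visit, and 6.4 schedules scans after SBRT without requiring continued avelumab. This is correct: the loss is from the primary analysis. But 15.5 names no population, patients never given SBRT have no schedule dated from it, and 6.7 promises only survival data after withdrawal.

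**Conclusion.** The concern holds. Section 15.4 conditions the primary RFS analysis on events after time zero, and the plan does not reconcile this with 11.2 and 15.7. That much is certain from the text.

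The numerical effect is not determinable, because neither the share of patients who stop after cycle 1 or miss SBRT nor their RFS is given. With one such patient the effect is small: the estimate rises by 0.6 to 1.1 points when that patient's RFS is 50% to 25%. With three it is material: 1.9 to 3.5 points, with a rejection rate of 0.16 to 0.23 (normal) or 0.12 to 0.19 (exact). These figures assume a true RFS of 80% and N = 50. There is no bias if excluded patients do as well as the rest. The definition should be corrected before RFS is analysed.

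**What to change.** In 15.4, define the primary RFS population as all eligible registered patients who received at least one avelumab dose, with RFS counted from the first dose. Keep the current set as a labelled sensitivity analysis, and state there whether SBRT means any fraction or all of them. This also preserves a comparison among patients who received SBRT, since the all-treated set can include some who did not. State in 11.2, 15.4 and 15.7 that this one rule governs RFS. Say how RFS is followed and censored in patients who stop early, including those never given SBRT.

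The cost is wording in three sections, a follow-up rule, and possibly some power. With RFS 90% in the retained patients and N = 50:

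| Excluded | Test | Restricted set | All treated, r = 0.80 / 0.50 / 0.25 |
|---|---|---|---|
| 1 | Normal | 73% | 72% / 67% / 63% |
| 1 | Exact | 63% | 60% / 54% / 50% |
| 3 | Normal | 72% | 69% / 53% / 41% |
| 3 | Exact | 67% | 56% / 39% / 26% |

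The normal rows use the formula above with n = 50 and p = (n_kept × 0.90 + k × r)/50; the exact rows sum the two binomials against the 45/50 rule. Part of the exact loss comes from the cut-off alone: at RFS 0.90 exact power is 0.671 with 47 patients but 0.616 with 50. The power stated in 15.2 should be rechecked for the all-treated population.

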### 15.5 Analysis of Secondary Objectives

- To determine whether SBRT combined with concurrent and adjuvant Avelumab results in improved loco-regional control, relapse free survival, and overall survival we will evaluate the recist criterion scans and survival rates at 6 months, 12 months and 24 months.
- To analyze whether SBRT combined with concurrent and adjuvant Avelumab impacts anti-tumor immune responses we will perform immunologic assays quantifying lymphocyte specificity and activation, including Immune cell Sequencing, ProtoArrays, Immunoassays, cell free DNA analyses, and multiparametric flow cytometry.
- Hazard rate estimates and 95% confidence intervals as well as Kaplan-Meier (KM) estimates will be used to summarize survival (OS), progression free survival (RFS), time to locoregional progression (TTLP) and time to distant progression (TTDP),

duration of response functions over time, and stable disease (SD). The median OS, PFS, TTLP, TTDP, and SD will be reported.

### **15.6 Evaluation of Toxicity**

All patients will be evaluable for toxicity from the time of their first treatment of CBI.

### **15.7 Evaluation of Response**

All patients included in the study must be assessed for response to treatment, even if there are major protocol treatment deviations or if they are ineligible. Each patient will be assigned one of the following categories: 1) complete response, 2) partial response, 3) stable disease, 4) progressive disease, 5) early death from malignant disease, 6) early death from toxicity, 7) early death because of other cause, or 8) unknown (not assessable, insufficient data).

All of the patients who met the eligibility criteria (with the possible exception of those who received no study medication) should be included in the main analysis of the response rate. Patients in response categories 4-8 should be considered to have a treatment failure (disease progression).

All conclusions should be based on all eligible patients. Sub-analyses may then be performed on the basis of a subset of patients, excluding those for whom major protocol deviations have been identified (e.g., early death due to other reasons, early discontinuation of treatment, major protocol violations, etc.). However, these sub-analyses may not serve as the basis for drawing conclusions concerning treatment efficacy, and the reasons for excluding patients from the analysis should be clearly reported. The reason for performing subset analyses would be to generate hypotheses for future prospective clinical trials.

## **16.0 STUDY MANAGEMENT**

---

### **16.1 Conflict of Interest**

Any investigator who has a conflict of interest with this study (patent ownership, royalties, or financial gain greater than the minimum allowable by their institution, etc.) must have the conflict reviewed according to UCSD conflict of interest policy.

### **16.2 Institutional Review Board (IRB) Approval and Consent**

The IRB should approve the consent form and protocol prior to any study-related activities. It is expected that the IRB will have the proper representation and function in accordance with federally mandated regulations.

In obtaining and documenting informed consent, the investigator should comply with the applicable regulatory requirement(s), and should adhere to Good Clinical Practice (GCP) and to ethical principles that have their origin in the Declaration of Helsinki.

Before recruitment and enrollment onto this study, the patient will be given a full explanation of the study and will be given the opportunity to review the consent form. Each

consent form must include all the relevant elements currently required by the FDA Regulations and local or state regulations. Once this essential information has been provided to the patient and the investigator is assured that the patient understands the implications of participating in the study, the patient will be asked to give consent to participate in the study by signing an IRB-approved consent form.

Prior to a patient's participation in the trial, the written informed consent form should be signed and personally dated by the patient and by the person who conducted the informed consent discussion.

### **16.3 Required Documentation**

Before the study can be initiated at any site, the following documentation must be provided to the UCSD Moores Cancer Center Clinical Trials Office

- ξ A copy of the official IRB approval letter for the protocol and informed consent.
- ξ A copy of the IRB-approved consent form.
- ξ CVs and medical licensure for the principal investigator and any associate investigators who will be involved in the study.
- ξ Form FDA 1572 appropriately filled out and signed with appropriate documentation. (NOTE: this is required if UCSD holds the IND. Otherwise, the affiliate Investigator's signature on the protocol is sufficient to ensure compliance)
- ξ CAP and CLIA Laboratory certification numbers and institution lab normal values.
- ξ Executed clinical research contract.

### **16.4 Registration Procedures**

All patients must be registered with the UCSD Moores Cancer Center Clinical Trials Office before enrollment to study. Prior to registration, eligibility criteria must be confirmed with the UCSD Study Coordinator . To register a patient, call [contact] Monday through Friday, 8:00AM-4:30PM. Study sites other than UCSD must fax informed consent documentation, completed eligibility checklist, and all source documentation for eligibility confirmation to the UCSD Clinical Trials Office ([contact]). Once eligibility is confirmed, patient will be given a unique sequential study number.

### **16.5 Subject Data Protection**

In accordance with the Health Information Portability and Accountability Act (HIPAA), subjects who have provided written informed consent must also sign a subject authorization to release medical information to the study Sponsor and allow a regulatory authority, or Institutional Review Board access to subject's medical information relevant to the study.

